**Table 5-1: Dosing Cohorts**

Cohort 1	22 subjects	200 mg KD025 QD
Cohort 2	22 subjects	200 mg KD025 BID
Cohort 3	22 subjects	400 mg KD025 QD
Cohort 4	22 subjects	600 mg/day KD025 (administered as 400 mg in the morning and 200 mg in the evening)
Cohort 5	22 subjects	Matching placebo BID

Abbreviations: BID = twice daily; QD = once daily

Study drug will be orally administered in a double-blind fashion.

During the 16 week, double-blind treatment period, data will be collected for the evaluation of efficacy of KD025.

All subjects will be given the option to receive KD025 400 mg QD for 32 weeks in an open-label treatment period. Safety, tolerability, and efficacy of KD025 will be evaluated for the remaining period in the study.

Subject status (relative to PASI) will be collected during the study for the evaluation of primary and secondary study endpoints. Response will be assessed by PASI, PGA, and DLQI scores at scheduled time points throughout the study.

All subjects will have PD blood samples collected over the course of the study.

Subjects will undergo medical history evaluations; PEs (including weight measurements); vital sign measurements; AE assessments; concomitant medication assessments; blood sample collection for hematology, chemistry, coagulation, lipid panel, and thyroid-stimulating hormone (TSH), urinalysis; pregnancy testing for females of childbearing potential; photography (optional); punch biopsy (optional); and ECGs. If a subject discontinues from the study prior to Week 16, an Early-Termination visit will be performed. All procedures are to be conducted immediately upon discontinuation.

For all subjects, including those who discontinue prematurely from the study, a Follow-Up visit will occur 30 days ( $\pm$  3 days) after the last dose of study drug.

See Table 1-1 (Schedule of Assessments) for specific assessment time points.

### **5.7 Randomization and Blinding**

This is a double-blind, randomized study. An Interactive Response Technology (IRT) system will be used for randomization and drug supply management.

## 6 STUDY POPULATION

### 6.1 Target Population

Approximately 110 adult male and female subjects (approximately 22 subjects per cohort) will participate in the study. Subjects will be eligible for enrollment as defined by the following inclusion and exclusion criteria.

### 6.2 Inclusion Criteria

To be eligible for participation in the study, each subject must meet all of the following criteria:

1. Adult, between the ages of 18 and 65 years
2. Able to provide written ICF prior to the performance of any study specific procedures
3. A diagnosis of moderate to severe chronic plaque psoriasis and is a candidate for systemic therapy or phototherapy
4. A PASI of  $\geq 12$  at screening and prior to the first dose of study drug, confirmed at Week 1 (Day 1)
5.  $\geq 10\%$  PASI body surface area involvement at screening and prior to the first dose of study drug, confirmed at Week 1 (Day 1)
6. Willing to avoid tanning devices
7. Adequate bone marrow function
  - a. Absolute neutrophil count (ANC)  $> 1500/\text{mm}^3$
  - b. Hemoglobin  $> 9.0 \text{ g/dL}$
  - c. Platelets  $> 100,000/\text{mm}^3$
8. Adequate safety laboratory values
  - a. Serum total bilirubin within normal limits (WNL)
  - b. AST and ALT  $< 2 \times$  upper limit of normal (ULN)
  - c. Serum creatinine  $< 1.5 \times$  ULN
9. Female subjects of childbearing potential have a negative pregnancy test at screening.  
Females of childbearing potential are defined as sexually mature women without prior

hysterectomy or those who have had any evidence of menses in the past 12 months.

However, women who have been amenorrheic for 12 or more months are still considered to be of childbearing potential if the amenorrhea is possibly due to prior chemotherapy, anti--estrogens, or ovarian suppression.

- Women of childbearing potential (i.e., menstruating women) must have a negative urine pregnancy test (positive urine tests are to be confirmed by serum test) documented within the 24-hour period prior to the first dose of study drug.
  - Sexually active women of childbearing potential enrolled in the study must agree to use 2 forms of accepted methods of contraception during the course of the study and for 3 months after their last dose of study drug. Effective birth control includes (a) intrauterine device plus one barrier method; (b) on stable doses of hormonal contraception for at least 3 months (e.g., oral, injectable, implant, transdermal) plus one barrier method; (c) 2 barrier methods. Effective barrier methods are male or female condoms, diaphragms, and spermicides (creams or gels that contain a chemical to kill sperm); or (d) a vasectomized partner.
10. For male patients who are sexually active and who are partners of premenopausal women: agreement to use 2 forms of contraception as in criterion 9, bullet 2c above, during the treatment period and for at least 3 months after the last dose of study drug
11. Willing to complete all study measurements and assessments in compliance with the protocol

### 6.3 Exclusion Criteria

Any subject who meets any of the following criteria will be ineligible for participation in the study:

1. Non-plaque or drug-induced (antimalarials, lithium) psoriasis (if subject is taking angiotensin II receptor blockers or beta blockers, doses must be stable for 6 months prior to study entry)
2. Use of systemic corticosteroid within 12 weeks prior to study entry
3. Use topical corticosteroids except to the face, groin, or scalp
4. Use of methotrexate, retinoids (such as acitretin), or calcineurin inhibitors (such as cyclosporine) within 4 weeks prior to study entry
5. Phototherapy within 4 weeks prior to study entry
6. Biologic therapies, including antibodies to IL-17, anti-TNF $\alpha$ , anti-IL-12 and IL-23, within 3 months prior to study entry
7. Current use of an inhibitor, inducer, or CYP3A4 (see Appendix G)
8. Active viral, fungal, or bacterial skin infection (other than nail fungal infection)
9. Is a pregnant or lactating woman
10. History of GI surgery including any bariatric surgery, or any GI condition that might interfere with drug absorption
11. Current participation in another study with an investigational drug or within 28 days or 5 half-lives of the investigational drug (whichever is longer) of study entry
12. History or other evidence of severe illness or any other conditions that would make the subject, in the opinion of the investigator, unsuitable for the study
13. Has QTc(F) interval (QT interval data corrected using Fridericia's formula) of > 450 msec (average of 3 readings) during screening (Appendix B)

14. Regular and/or excessive use of alcohol within the 2 years prior to study entry defined as alcohol intake > 14 drinks per week in a man or > 7 drinks per week in a woman. Approximately 10 g of alcohol equals one “drink” unit. One unit equals 1 ounce of distilled spirits, one 12-ounce beer, or one 4-ounce glass of wine.
15. Exposure to KD025 within the last 6 months prior to study entry, or known allergy/sensitivity to KD025 or any other ROCK-2 inhibitor
16. History or presence of any of the following:
  - a. ALT or AST >  $2.0 \times$  ULN at screening. (Subjects with an isolated AST elevation of any magnitude, or a ratio of AST:ALT > 1.5 should be interviewed regarding use of alcohol, have levels repeated and participation in the study should be discussed with the medical monitor.)
  - b. Renal disease and/or serum creatinine >  $1.5 \times$  ULN at screening

## 7 STUDY ASSESSMENTS AND PROCEDURES

Screening assessments outlined in this section and in Table 1-1 will be performed after obtaining a signed ICF.

The timing for these study assessments is presented in Table 1-1 while a listing of clinical laboratory parameters to be measured is presented in Table 7-1.

### 7.1 General Study Procedures

A description for each phase of the study is provided in this section.

Confirmation that the most current IRB/IEC-approved ICF has been signed should occur before any study-specific procedures are performed. All subjects who are enrolled and receive KD025 or undergo study-specific procedures should be re-consented with any updated versions of IRB/IEC-approved ICFs during study participation as applicable and per institutional guidelines.

#### 7.1.1 Screening Enrollment

Informed consent must be obtained before completing any study-specific procedures.

After written informed consent has been obtained, subjects will be screened to assess eligibility for study participation. All screening assessments are to be performed within **28 days** prior to first study drug dose, unless otherwise specified.

If significant changes from baseline are noted during the course of the study, additional unscheduled clinic visits may be undertaken by the investigator, or requested by the sponsor, in order to determine both the relevance of the finding(s) and the duration of the event(s).

Subjects who meet the eligibility criteria will be eligible to be enrolled in the study.

#### 7.1.2 Double-Blind Treatment Period

Study Day 1 is defined as the date the subject takes the first dose of study drug, with subsequent visits numbered sequentially thereafter. Subjects satisfying eligibility requirements will be enrolled and should receive the first dose of study drug on Day 1 of the study.

Procedures will be completed during the treatment period from Week 1 to Week 16 at the times designated in the Schedule of Assessments (Table 1-1).

### **7.1.3 32-week Open-Label Continuation Period**

Procedures will be completed during the 32-week continuation period from Week 16 (after the completion of assessments in the double-blind treatment period) to Week 48 at the times designated in the Schedule of Assessments (Table 1-1).

### **7.1.4 Early-Termination Visit**

An Early-Termination visit will be scheduled for all subjects who discontinue prematurely from the study during the double-blind or open-label treatment periods and procedures are to be conducted immediately upon discontinuation (refer to Table 1-1).

### **7.1.5 Unscheduled Visit**

Unscheduled visits and the assessments performed at those visits are at the investigator's discretion, but may include any or all of those listed in Table 1-1.

### **7.1.6 30-day Follow-up Visit**

Approximately 30 days ( $\pm 3$  days) after the subjects last dose of study drug, all subjects will complete a 30-day Follow-Up visit (Table 1-1).

## **7.2 Description of Study Procedures**

Refer to Table 1-1 for an outline of the procedures required at each study visit. Informed Consent Form.

All subjects must take part in the ICF process. Adequate time must be allowed for the subject to ask questions and make a voluntary decision. No protocol-specific procedures, including screening procedures, are to be performed until the subject has signed and dated an IRB/IEC-approved ICF.

### **7.2.1 Demographics and Medical History**

A complete medical history will include demographic information, prior medical illnesses and conditions, and surgical procedures.

### **7.2.2 Physical Examination**

Physical examinations (PE) will include assessment of skeletal (i.e., muscle aches), neurological (i.e., gait) systems, height (screening only) and weight. All procedures will be performed by a physician or staff member who is qualified to perform such examinations (e.g., physician's assistant, nurse practitioner).

Any abnormal or clinically significant findings from the PE must be recorded in the appropriate electronic case report form (eCRF).

### **7.2.3 Vital Sign Measurements**

Vital sign measurements will be collected after the subject has been sitting for 5 minutes. Vital sign assessments will include measurements of a sitting BP (mmHg), heart rate (beats per minute), respiratory rate (breaths per minute), and temperature (Fahrenheit).

Note that BP measurements are to be performed using appropriate technique (per guidelines of the American Heart Association). Subjects must be seated quietly for at least 5 minutes in a chair with their backs supported, feet flat on floor (legs uncrossed), and arms bared on a hard surface, with the arm slightly abducted and bent, with palm up and the midpoint of upper arm at heart level. Correct cuff and bladder size should be utilized. Two or more readings separated by 1 to 2 minutes should be averaged. If the first 2 readings differ by more than 5 mmHg, additional readings should be obtained and averaged. Record cuff size, arm used, and subject's position (if not seated).

### **7.2.4 Laboratory Assessments**

A central laboratory will analyze hematology, serum chemistry, coagulation, lipid panel, TSH, urinalysis, and biomarker tests. The results will be provided to the investigator (Table 7-1). Blood and urine samples for hematology, serum chemistry, coagulation, lipid panel, TSH, antibody, and urinalysis will be obtained using standard procedures.

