  - k. On Day 1 (Week 1), prior to dosing, subjects will be randomized to receive 200 mg KD025 once daily (QD), 200 mg KD025 twice daily (BID), 400 mg KD025 QD, 600 mg/day KD025, or matching placebo. On Day 112 (Week 16) after all assessments are complete in the double-blind treatment period, subjects will be given the option to continue in the 32-week open-label treatment period, during which all participating subjects will receive KD025 400 mg QD for 32 weeks.
  - l. Photos will be taken of affected area(s) if the subject agrees to them. Detailed instructions will be provided.
  - m. Punch biopsies from clear unaffected skin and a selected lesion will be collected predose on Day 1 (Week 1) and from the selected lesion on Day 112 (Week 16). Subjects have the option to decline the punch biopsy.
  - n. PD blood samples to be collected predose and 6 hours postdose on Day 1 of Weeks 1 and 8. PD blood samples to be collected predose on Day 1 of Week 16; predose on Day 1 of Week 48 (for those subjects receiving KD025 during the 32-week continuation period), and at the 30-Day Follow-Up visit.
  - o. To be eligible for the study, subjects must have a PASI of  $\geq 12$  at screening and prior to the first dose of study drug, confirmed at Day 1 (Week 1).
  - p. Subjects will take the first dose of study drug in the clinic and at each visit when PD blood samples are collected. Then study drug will be dispensed for home administration. Study drug is to be taken with a meal or within 5 minutes of finishing a meal.
  - q. Subjects will be required to keep study drug diaries in which they will record the date of study drug administrations. These diaries will be dispensed at the Day 1 (Week 1) visit. Final collection will be at Week 16 for those who do not wish to continue into the open-label period. For subjects that continue to the open-label treatment period, a new diary will be distributed at the Week 16 visit and will be collected at the Week 48 visit. For subjects who discontinue the study prematurely, the diary will be collected at the Early-Termination visit.

---

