#### **4.1 Study Rationale**

This proof-of-principle, placebo-controlled study is designed to evaluate the efficacy, safety, and tolerability of KD025 administered orally for 16 weeks to subjects with moderate to severe chronic plaque psoriasis who are candidates for systemic therapy or phototherapy. Data collected in this study will be used along with data from previous KD025 studies to further evaluate the safety, tolerability, and efficacy of KD025.

Recent studies with KD025 have demonstrated that this molecule has anti-inflammatory activity mediated by the inhibition of secretion of IL-17 and IL-21 by Th17 cells. Since this pathway has emerged as a central inflammatory pathway in psoriasis, it is possible that an oral formulation (e.g., KD025) could offer significant advantages over other available oral formulations. This study will provide safety and efficacy data of the therapeutic response to evaluate the risk/benefit of treating plaque psoriasis with KD025.

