#### **4.2 Selection of Doses in this Study**

The only Rho kinase inhibitor that has published human dosing data is fasudil. Fasudil is a moderately selective kinase inhibitor but in contrast to KD025 has activity against both Rho-associated, coiled-coil-containing protein kinase (ROCK1 and ROCK2). The potency of fasudil against ROCK2 is similar to KD025. Fasudil has been marketed in Japan for more than 10 years as an intravenous drug for the prevention of cerebrovascular spasm after stroke. Fasudil was also under development for the treatment of chronic angina. In a Phase 2 clinical study in the US (Vicari et al, 2005), fasudil was dosed from 20 mg three times a day (TID) up to 80 mg TID over 8 weeks. At all doses tested, the adverse events (AEs) in the treatment arm were

reported as no different from placebo. In a separate study to examine endothelial function in subjects and healthy subjects (Nohria et al, 2006), fasudil was dosed at 40 mg TID for 30 days.

The single-ascending dose (SAD)/multiple-ascending dose (MAD) (KD025-101) and MAD (KD025-102) studies support daily dosing with KD025 and have shown a safety profile that allows daily dosing up to 1000 mg per day. In addition, in Study KD025-103, a Phase 1, placebo-controlled study examining the safety, tolerability, and pharmacokinetics (PK) of 500 mg of KD025 administered BID for 28 days in healthy male and post-menopausal female subjects for up to 28 days, the regimen was generally well tolerated.

Pharmacodynamic (PD) studies in these normal healthy subjects have shown biological activity in inhibition of secretion of IL-17 and IL-21 by TH-17 cells in ex vivo stimulated peripheral blood mononuclear cells at the 120-, 240-, and 320-mg dose levels. Thus, the dosing selected in the proposed study (200 mg once daily [QD], 200 mg BID, 400 mg QD, and 600 mg/day) should be both safe and at a level at which biological activity has been measured.

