### **7.2.9 Blood Sampling for Pharmacodynamics**

Blood sample collection for PD will be performed at all sites (refer to Table 1-1 for time points). All subjects will have PD blood samples collected over the course of the study. Subjects who elect to continue therapy will also have PD blood samples collected.

For any subject who discontinues prematurely, blood for PD evaluation will be collected at the Early Termination visit.

Samples will be evaluated for the expression of the psoriasis-associated cytokine, IL-17, in plasma. Detailed instructions for sample collection and preparation will be provided in a separate manual.

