#### **7.2.11 Relative Physician's Global Assessment**

The relative PGA documents the physician's assessment of the subject's psoriasis status (Robinson 2012). Consideration should be given to the percent of body involvement as well as overall induration, scaling, and erythema (refer to Appendix C).

The DLQI is a skin disease-specific instrument designed to assess the impact of the disease on a subject's quality of life (Finlay et al, 1994). Refer to Appendix D for the complete questionnaire.

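### IL-17 results go to the blinded investigator with no withholding rule or release time, which leaves open a possible route to unblinding the Week 12 and Week 16 PASI and PGA scoring

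*Protocol*

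**What the plan says.** Protocol 7.2.4 puts biomarkers in the same list as the safety laboratory tests and applies one reporting rule to all of them: "urinalysis, and biomarker tests. The results will be provided to the investigator (Table 7-1"). Table 7-1 has a Biomarkers box with a single entry, IL-17.

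Protocol 7.2.9 says what is measured in the pharmacodynamic (PD) blood samples: "Samples will be evaluated for the expression of the psoriasis-associated cytokine, IL-17, in plasma". All subjects are sampled. Footnote n of Table 1-1 gives the times: "PD blood samples to be collected predose and 6 hours postdose on Day 1 of Weeks 1 and 8", and then "PD blood samples to be collected predose on Day 1 of Week 16". The same table schedules PASI and PGA at Weeks 4, 8, 12 and 16 of the double-blind period.

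Protocol 4.1 attributes to KD025 "anti-inflammatory activity mediated by the inhibition of secretion of IL-17 and IL-21 by Th17 cells".

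On blinding, Protocol 5.7 says the study is double-blind and names the interactive response system for randomization and drug supply. Protocol 11.3.9.4 says the investigator stays blinded, but in the setting of code breaks for expedited safety reports. The SAP Introduction says PD data are analysed and reported separately.

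**The concern.** The protocol tells the investigator that the drug acts on IL-17 and also provides that investigator with IL-17 results. If those results arrive during the double-blind period and plasma IL-17 responds to the drug, a falling profile would suggest active treatment and a flat one placebo.

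The endpoints at stake depend on clinical judgement. Protocol 7.2.10 builds PASI from 0–4 sign grades and estimated area bands. For the PGA, 7.2.11 says "The relative PGA documents the physician's assessment of the subject's psoriasis status". No independent assessor, and no assessor kept from laboratory results, is named for either scale. A scorer who suspects the arm could grade active subjects lower and placebo subjects higher. That would favour KD025 on the primary PASI 75 comparison and on the PGA.

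**Working it through.** The plan gives no figure on this point to reproduce. The check has three parts: whether the route exists on the text, whether the timing allows it, and what a scoring shift would do.

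**1. Is there a safeguard anywhere?**
- Protocol 7.2.4 makes no exception for biomarkers.
- Protocol 5.7 covers only the randomization system.
- Protocol 7.2.9 refers to a separate manual for sample collection and preparation. It does not mention release of results.
- Protocol 11.3.9.4 confirms that the investigator is meant to be blinded, but does not mention PD results.
- The SAP Introduction concerns where PD data are analysed, not whether subject-level values go to sites.
- Protocol 11.3.10 asks that all laboratory data obtained during the study be reviewed, with no exception for IL-17.
- No eligibility, stopping or liver rule (6.2, 6.3, 8.2, 9.4) uses IL-17, so the investigator does not need the value for any of them.

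**2. Timing, from Table 1-1**

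Week 8 is Day 56, Week 12 is Day 84 and Week 16 is Day 112, each ±3 days.
- Week 8 to Week 12: 84 − 56 = 28 days; minimum (84 − 3) − (56 + 3) = 22 days.
- Week 8 to Week 16: 112 − 56 = 56 days; minimum (112 − 3) − (56 + 3) = 50 days.
- Samples drawn before Week 12: predose Week 1 (baseline), 6 hours postdose Week 1, and predose and 6 hours postdose Week 8. That is one baseline value and three values after the first dose.
- The Week 16 sample is drawn at the primary scoring visit, so its result is unlikely to precede that scoring.

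A turnaround of about three weeks would put Week 8 values with the site before both scorings. A batch assay after the last Week 16 visit would put none there. The documents give no turnaround.

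**3. Sensitivity to a scoring shift (illustration only)**

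With 22 per cohort (Table 5-1), one subject is 1/22 = 4.5 percentage points. For *a* versus *b* responders and t = a + b, each table has probability C(22,a)·C(22,t−a)/C(44,t). The two-sided Fisher p-value sums the tables no more likely than the one observed. For 7 v 1:
- 2 × [C(22,7)·C(22,1) + C(22,8)] / C(44,8)
- = 2 × (3,751,968 + 319,770) / 177,232,627 = 0.0459.

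| Responders out of 22, KD025 v placebo | p before | p after |
|---|---|---|
| 6 v 1 becomes 7 v 1 | 0.0946 | 0.0459 |
| 7 v 2 becomes 7 v 1 | 0.1324 | 0.0459 |
| 4 v 1 becomes 5 v 1 | 0.34 | 0.19 |
| 8 v 1 becomes 9 v 1 | 0.02 | 0.009 |

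The first two rows cross 0.05 and the last two do not.

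Suppose next that the true PASI 75 rate is 5% in both arms (the placebo rate in SAP 3.12) and that scoring inflates the active rate by b. The rejection probability for one comparison is the sum of Bin(i; 22, 0.05 + b) × Bin(j; 22, 0.05) over all (i, j) with Fisher p ≤ 0.05.

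| Assumed inflation b | Rejection probability |
|---|---|
| 0 points | 0.3% |
| 5 points | 2.2% |
| 10 points | 8.8% |
| 15 points | 20.2% |

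The values of b are assumptions; the documents give no basis for choosing among them.

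**The case against.** The strongest reply is that harm needs three links, none of them documented: results released before scoring, plasma IL-17 that discriminates between arms, and scoring that changes as a result.

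- **Timing.** A reader might infer from the schedule that sites will hold IL-17 values when they score Weeks 12 and 16. The documents do not support that. They date the draws, not the results, and exploratory samples may be assayed in batch at the end. The SAP's separate reporting of PD data, the silence of 7.2.9 on returning results, and the absence of biomarkers from the next sentence of 7.2.4 (on how samples are obtained) all suggest that IL-17 may not follow the routine safety stream. This objection stands against saying that results *will* arrive early. It does not remove the sentence in 7.2.4 or supply a withholding rule.
- **Discrimination.** A reader might also treat plasma IL-17 as a direct read-out of treatment. The human evidence in Protocol 4.2 is secretion by Th17 cells from healthy subjects, "in ex vivo stimulated peripheral blood mononuclear cells at the 120-, 240-, and 320-mg dose levels". The trial measures plasma in patients, and change in IL-17 is itself an exploratory objective. This objection stands: the marker belongs to the stated mechanism, but nothing shows that it classifies an individual.
- **Magnitude.** The one-subject examples that cross 0.05 are selected, and other one-subject shifts do not cross it. They show that a small trial is sensitive to single scores, not that IL-17 release moves any score. This also stands.

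**Conclusion.** The point holds in a limited form. As written, Protocol 7.2.4 with Table 7-1 provides IL-17 results to a blinded investigator, and neither document sets a release time or withholds them. Week 1 and Week 8 results could therefore arrive before the Week 12 and Week 16 PASI and PGA scoring. That is a possible route to unblinding, opened by a stated rule.

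The documents do not show that any result was or will be released early, or that the blind is broken. The bias would be nil if samples are assayed after scoring, if plasma IL-17 does not separate the arms, or if scorers do not act on it. If all three links hold, the primary endpoint and the PGA are exposed in the direction that favours KD025. Its size cannot be estimated from the documents; the inflation figures above are conditional on assumed shifts. This should be fixed because the remedy is nearly free, not because bias has been demonstrated.

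**What to change.** In Protocol 7.2.4 and Table 7-1, exclude biomarker tests from the results returned to the investigator. Add a sentence on these lines: post-baseline IL-17 (PD) results are withheld from sites and from blinded sponsor staff until the Week 16 database is locked. Instruct the central laboratory to suppress IL-17 from site reports. The Week 16 lock is already named in Protocol 12.7.

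The rule need not extend to biopsy markers for this purpose. The only post-baseline biopsy is at Week 16, so it adds little to the risk before scoring.

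Both Protocol 12.2 and SAP 3.12 describe early termination at 110 subjects, so a prospective sentence may come too late for some or all scoring. If Week 16 scoring is complete, document from the laboratory's reporting records whether any IL-17 results reached sites before the Week 12 or Week 16 assessments, and report the answer with the efficacy results.

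The cost is one protocol sentence, a table note and a laboratory reporting setting. No eligibility, stopping or liver rule uses the value, so withholding it affects none of them.
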